8.3. Preparation and Handling

The investigative site will receive bottles of blinded study drug. The Investigator may delegate study drug handling to site staff who will dispense bottles of study drug for subject administration according to the interactive response technology system. The interactive response technology system is being utilized to ensure the correct distribution of blinded study drug according to the randomization schedule. The maintenance of treatment randomization codes will be maintained within the IRT system.

The investigative site will receive bottles of acetaminophen rescue medication, and there will be no rescue medication preparation done at the investigative site. The Investigator may delegate rescue medication management to site personnel who will dispense bottles of rescue medication for subject administration according to the IRT system. The IRT system will be utilized to ensure the correct distribution of rescue medication.

8.4. Storage

Study drug should be stored in a locked, limited access location according to the label. The capsules should be stored at 20°C to 25°C, with excursions permitted between 15°C to 30°C. The investigative site should contact the Sponsor for directions regarding nonpermitted excursions.

Rescue medication should be stored in a locked, limited access location according to the label. The tablets should be stored at 20°C to 25°C. The investigative site should contact the Sponsor for direction regarding excursions.

8.5. Accountability

The Investigator or designee at the investigative site will conduct study drug accountability. The investigative site personnel will receive, inspect, and acknowledge condition of study drug and rescue medication; document the amount received, dispensed and returned; and maintain the study drug accountability records. A Sponsor's representative will inspect study drug and accountability records. Site personnel will conduct subject -level accountability, account for and document used/unused study drug and rescue medication, and the site will retain bottles of returned study drug and rescue medication in the investigative site's limited access storage area.

Upon completion or termination of the study and after Sponsor's accountability is completed, all used and unused study drug and containers will be returned to the depot as instructed by the Sponsor's representative. All used and unused rescue medication and containers may be destroyed at the site or returned to the depot as instructed by the Sponsor's representative.

8.6. Treatment Compliance

Site personnel will assess subject compliance with study drug dosing and rescue medication use via pill count and discussion with the subject. In addition, incorrect doses will be documented.

8.7. Concomitant and Excluded Medications

Subjects will discontinue any current analgesic medicationstaken for pain related to fibromyalgia, with the exception of acetaminophen (rescue medication). Rescue medication may be taken for pain related to fibromyalgia only. Stable doses of the benzodiazepines alprazolam and lorazepam will be allowed for the treatment of anxiety. The benzodiazepine receptor agonists, zolpidem (immediate-release) and zaleplon as well as melatonin, ramelteon and low-dose trazodone will be allowed for the treatment of sleep disturbances. Stable doses of serotonin-specific reuptake inhibitors (SSRIs) will be allowed. Intermittment use of triptans for treatment of migraines is permitted.

Concomitant use of antiepileptic drugs, gabapentinoids, mood stabilizers, nonsteroidal anti-inflammatory drugs (NSAIDs [except cardiac preventive low dose acetylsalicylic acid]) outside of infrequent use for pain unrelated to fibromyalgia as described below, systemic corticosteroids, opioid or narcotic analgesics, muscle relaxants, tramadol, injected or topical lidocaine, injected or topical capsaicin, selective norepinephrine reuptake inhibitors (SNRIs), tricyclic (TCAs [except low-dose cyclobenzaprine]), and tetracyclic (TeCAs) antidepressants, monoamine oxidase inhibitors (MAOIs), psychostimulants, sodium oxybate, benzodiazepines (except alprazolam or lorazepam), barbiturates, or NMDA receptor ligands (e.g., ketamine, esketamine, amantadine, dextromethorphan [except low dose intermittent use for cough] memantine, methadone, dextropropoxyphene or ketobemidone) is prohibited.

A positive urine drug screen for benzodiazepines or opioids inconsistent with current prescriptions, psychoactive cannabinoids (e.g., marijuana, THC) inconsistent with subject reported use, PCP, cocaine or amphetamines is exclusionary at Visit 1.

A positive urine drug screen for benzodiazepines inconsistent with protocol specified allowed prescriptions, psychoactive cannabinoids (e.g., marijuana, THC) inconsistent with subject reported use, opioids, PCP, cocaine or amphetamines is exclusionary at Visit 2.

If it is questionable whether a medication(s) falls into the category of excluded medications named above, the Investigator should review the medication with the Sponsor prior to the enrollment of the subject. Washout from excluded medication for fibromyalgia is allowed only if the Investigator deems it is medically appropriate. The washout must be completed within the duration of the Screening Period with the last dose being at least two (2) weeks prior to randomization (See Section 15.1 of the protocol for Disallowed Analgesic and Other Medications).

Subjects will be dispensed acetaminophen to be used as rescue medication and will be instructed to take no more than 3 g/day (one to two 500 mg tablets every 6 hours as needed) for pain related to fibromyalgia. Rescue medication will be provided by the Sponsor.

For pain unrelated to fibromyalgia, subjects may use a nonsteroidal anti-inflammatory drug (NSAID) for up to two (2) days during a seven (7) day period. If the need for analgesics exceeds this period, the patient should call the Investigator to evaluate the cause of pain and the course of action. If a subject requires a NSAID for pain unrelated to fibromyalgia, the medication should be recorded as a concomitant medication and the adverse event must be recorded in the eCRF.

Medications used within 30 days prior to screening through the end of treatment in this study must be documented in the source documents and on the corresponding electronic case report form (eCRF).

9. STUDY ASSESSMENTS AND PROCEDURES

9.1. Screening Assessments

9.1.1. Medical History

Medical history will be documented based on subject report and investigator's assessment.

9.1.2. American College of Rheumatology Fibromyalgia Criteria

The 2016 American College of Rheumatology Fibromyalgia Criteria is a patient survey that is used as a diagnostic tool for fibromyalgia. The diagnostic criteria for fibromyalgia are met by the following 3 conditions [Wolfe 2016]:

- Widespread Pain Index ≥ 7 and Symptom Severity Score ≥ 5 , or the Widespread Pain Index is 4 to 6 and the Symptom Severity Score is ≥ 9 .
- Symptoms have been present at a similar level for ≥ 3 months; and
- Pain is generalized and present in at least 4 of 5 regions.

All subjects will be assessed for widespread pain symptoms using these criteria.

9.1.3. Mini-International Neuropsychiatric Interview (MINI)

The MINI is designed as a brief structured diagnostic interview to meet the need for a short but accurate structured psychiatric interview for multicenter clinical trials. The standard MINI version 7.0.2 for DSM-5 will be used in this study to assess the 17 most common disorders in mental health. The disorders investigated are the most important to identify in clinical and research settings. The disorders were selected based on current prevalence rates of 0.5% or higher in the general population in epidemiology studies [Sheehan 1998].

9.2. Efficacy Assessments

9.2.1. Numeric Rating Scale of Pain Intensity (NRS)

The NRS of pain intensity is a unidimensional, segmented numeric version of the visual analog scale. A subject selects a whole number (0 to 10) that best indicates the intensity of his/her pain. The format consists of a horizontal line which is anchored by terms defining pain levels, where 0 represents no pain and 10 represents worst possible pain.

Subjects will report, at bedtime, their average pain intensity during the past 24 hours using the 11-point NRS.

9.2.2. Daily Sleep Interference Scale (DSIS)

The DSIS was developed to quantify sleep interference due to pain. The DSIS is a single item measure that is completed by patients once a day (upon awakening) to accurately capture variability in sleep interference due to pain on a daily basis, thus minimizing recall bias. The DSIS has an 11-point response scale that asks patients to “Select the number that best describes how much your pain has interfered with your sleep during the past 24 hours.” Response options range from 0 (Did not interfere with sleep) to 10 (Completely interfered with sleep/unable to sleep due to pain). The DSIS is designed to be used in a patient daily diary that patients fill out upon awakening each morning [Vernon 2008].

9.2.3. Fibromyalgia Impact Questionnaire – Revised (FIQR)

The FIQR is an updated version of the Fibromyalgia Impact Questionnaire, which is an assessment of the physical functioning, work status, depression, anxiety, morning tiredness, pain, stiffness, fatigue, and well-being in fibromyalgia subjects measured over the period of one week. The FIQR differs from the Fibromyalgia Impact Questionnaire in that it includes questions on memory, tenderness, balance and environmental sensitivity as well as modified function questions [Bennett 2009].

9.2.4. Patient Reported Outcomes Measurement Information Systems – Fibromyalgia PROMISFM – Fatigue Profile– Short Form

The PROMISFM fatigue profile is a 16-question instrument that has four 4-item short forms that examine the intensity of the impact of fatigue in social, cognitive, and motivation subdomains [Kratz 2016].

[figure not shown]
9.2.5. Patient Reported Outcomes Measurement Information Systems – Fibromyalgia PROMISFM – Sleep Disturbance – Short Form

The PROMIS_{FM} Sleep Disturbance short form is an 8-item instrument that assesses sleep disturbance in subjects 18 years and older [Yu 2011].

9.2.6. Patient Reported Outcomes Measurement Information Systems – Fibromyalgia PROMISFM – Physical Function – Short Form

The PROMIS_{FM} physical function – short form measures the self-reported performance of physical activities including dexterity, walking or mobility and the ability to complete activities of daily living [Driban 2015].

9.2.7.

9.2.8. Patient Global Impression of Severity (PGI-S)

PGI-S is a global index used to rate the severity of a specific condition (a single-state scale), on which (1) corresponds to “no pain”, two (2) corresponds to “mild”, three (3) corresponds to “moderate” and four (4) corresponds to “severe”.

9.2.9. Patient Global Impression of Change (PGI-C)

The PGI-C allows subjects to rate the change in the disease state from study initiation to specific time points during the study or at the end of the study. It provides the subject’s impression of overall change since beginning the study on a 7-point scale on which one (1) corresponds to “very much improved”, four (4) corresponds to “no change” and seven (7) corresponds to “very much worse”.

9.3. Safety Assessments

9.3.1. Safety Parameters

Refer to the [Table 3](#) (Schedule of Procedures) or [Section 10](#) (Schedule of Procedures) for time points.

9.3.2. Vital Sign Measurements

Each assessment includes blood pressure and pulse after at least five (5) minutes of being seated or lying supine, and prior to blood sample collection. Vital signs may be repeated up to three (3) times at screening, per the Investigator’s discretion. There should be a minimum of five (5) minutes of rest allotted in between measurements. All vital signs should be recorded in the

subject's source documents, with the final measurement of vital signs being entered into the eCRF system.

9.3.3. Physical Examination

A complete physical examination will include assessment of the following body systems: head, eyes, ears, nose, and throat, lymph nodes, neurologic, respiratory, cardiovascular, gastrointestinal, musculoskeletal, dermatologic systems and extremities.

The complete physical examination at Visit 1 will include a comprehensive neurological examination of the following components: cranial nerves, muscle strength and tone, sensory function, coordination, gait, reflexes and mental status.

The brief physical examination may be completed at Week 12 or the Early Termination Visit.

For measuring weight, a calibrated scale with appropriate range and resolution will be used. Subjects must remove shoes and bulky layers of clothing.

Height will be measured without shoes.

9.3.4. Electrocardiogram

TriPLICATE electrocardiograms will be collected at screening after five (5) minutes of supine rest and prior to blood sample collection, if possible. There should be a minimum of a two minute interval between ECGs. The device will be a Spaulding (Spaulding Medical, West Bend, WI) electrocardiogram device that acquires a 12-lead electrocardiogram. The electrocardiogram data will be submitted to the designated electrocardiogram laboratory cardiologists for measurements and diagnoses.

The Investigator or qualified Subinvestigator will review all electrocardiogram interpretations and interval duration measurements for clinical significance. Standard electrocardiogram parameters will be measured. Clinically significant, abnormal 12-lead electrocardiograms should be repeated. Clinically significant electrocardiogram changes should be recorded as an adverse event.

The Spaulding electrocardiogram device should be used for all assessments during the study unless it is nonoperational, in which case another electrocardiogram may be performed locally and transmitted to Spaulding for central reading via printout.

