- p Urine drug screen kit for local testing.
- q Includes prior medications taken within the last 30 days.
- r Adverse events will be collected from the time of study drug administration through the last day of the subject's participation in the study. Serious adverse event reporting will begin at the time informed consent is obtained and will end 30 days after last dose of study drug.
- s To be completed by Investigators or qualified Subinvestigators when potential abuse-related events are identified and upon the completion of each subject's participation in the study.
- t Subjects will complete the PROMIS_{FM} sleep disturbance, fatigue profile and physical function short form questionnaires.
- u Screening ECGs will be collected in triplicate (at least two (2) minutes apart). All other ECGs will be single ECGs.
- v Visit Three (3) will be completed by telephone or videoconference. The subject will be asked to complete the printed copy of the S-STS given to them at their Baseline Visit while communicating with the site staff. The staff will review the subject's answers to the S-STS and recommend corrections, only where the form has been completed incorrectly. The completed S-STS source document will be mailed back to the clinic or returned at the next study visit to be filed in the subject's chart and entered into the eCRF system.
- w To be measured without shoes.
- x To be obtained with a calibrated scale and subject must remove shoes and bulky layers of clothes.
- y A safety follow-up call should be completed 7-10 days after Visit 6 completion. Final safety follow-up call to be made 30 (±5 days) days after Visit 6 completion. Investigator may ask subject to return for Unscheduled Visit, as needed.

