7.2. Subject Exclusion Criteria

Exclusion Criteria:

Subjects who meets ANY of the following criteria will be excluded from the study:

1. Lifetime history of any psychotic and/or bipolar disorder.
2. Subjects with uncontrolled major depressive disorder or generalized anxiety disorder, in the investigator's opinion. (subjects may have been on a stable protocol allowed medication for greater than 60 days prior to screening) or are not expected to remain stable for the duration of the study.
3. Pain due to diabetic peripheral neuropathy, post-herpetic neuralgia, traumatic injury, prior surgery, complex regional pain syndrome, or other source of pain that, in the investigator's opinion, would confound or interfere with the assessment of the subject's fibromyalgia pain or require excluded therapies during the subject's study participation.
4. Pain due to concurrent autoimmune, infectious, or inflammatory disease such as rheumatoid arthritis, systemic lupus erythematosus, ankylosing spondylitis, psoriatic arthritis, inflammatory bowel disease, or other chronic widespread pain condition(s) that may confound fibromyalgia pain reporting.
5. Any impairment, activity or situation that, in the judgment of the Investigator, would prevent satisfactory completion of the study protocol.

6. An untreated endocrine disorder that may confound fibromyalgia assessments.
7. History of severe renal impairment defined by currently receiving hemodialysis or peritoneal dialysis or has undergone a previous renal transplant.
8. Known history of significant cardiovascular condition, such as myocardial infarction within the past year, or moderate to severe congestive heart failure (New York Heart Association [NYHA] Class III and IV); evidence of current uncontrolled cardiac arrhythmias, angina; or electrocardiographic evidence of acute ischemia or clinically significant conduction system anomalies; QTcF >450 msec (males) or >470 msec (females); or uncontrolled hypertension characterized by resting systolic blood pressure >160 mm Hg or resting diastolic >100 mm Hg, or clinically significant hypotension in the judgement of the Investigator as characterized by resting systolic blood pressure <90 mm Hg or resting diastolic blood pressure <60 mm Hg accompanied by symptoms such as lightheadedness, dizziness, and profound fatigue or signs such as irregular heartbeat.
9. Resting pulse rate <45 bpm or >95 bpm.

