6.2.2 Baseline

Baseline is defined as the last non-missing value (either scheduled, unscheduled or repeat) before the subject receives the first dose of study drug.

For endpoints in which the weekly mean is being utilized, baseline is defined as the average of the available assessments on the last 7 days prior to the first dose of study drug (study days -7 to -1).

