6.2.10 Electrocardiogram (ECG) Data

For electrocardiogram (ECG) data recorded on continuous scales, if more than one value (for instance, triplicate recordings) is recorded at a time point (i.e., date), the mean value rounded to the integer will be presented. in the event that one reading is missing, the average of the available two readings will be used for the analysis. Furthermore, if only one reading is available, this reading will be used for the analysis.

For overall interpretation if more than one interpretation is recorded, the most severe (worst case) interpretation will be presented.

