6.2.12 Unscheduled Visits

Unscheduled visits will be handled in an identical manner to early withdrawal assessments. If this results in multiple records for a given visit, then the scheduled visit will take highest precedence, followed by early withdrawal visits, and unscheduled visits last.

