6.12.4 Electrocardiogram Data

Descriptive statistics for observed values and changes from baseline in the following ECG variables will be tabulated at each post-baseline visit:

- Heart rate (bpm)
- PR interval (ms)
- RR interval (ms)
- QRS complex (ms)
- QT interval (ms)
- QTc interval (ms) [Bazett's formula - QTcB]
- QTc interval (ms) [Fridericia's formula - QTcF]

Shift tables in relation to the overall interpretation (Normal, Abnormal Not Clinically Significant [NCS], and Abnormal Clinically Significant [CS]) from baseline to each post-baseline visit will be presented.

All ECG assessments throughout the study will be listed.

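### SAP 6.2.10 averages a same-date for-cause repeat ECG with the tracing that triggered it, and no planned table counts QTcF above a threshold by arm

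*Protocol*

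**What the plan says.** **Collection.** Table 3, footnote u, of the protocol: "Screening ECGs will be collected in triplicate (at least two (2) minutes apart). All other ECGs will be single ECGs". The on-treatment ECGs are at Weeks 4, 8 and 12 (Protocol 10.3.2 and 10.3.3).

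**Repeats.** Protocol 9.3.4: "Clinically significant, abnormal 12-lead electrocardiograms should be repeated". The trigger is clinical significance, not a QTcF value, and no timing is given. Clinically significant changes are also recorded as adverse events (9.3.4) and summarised as TEAEs (12.7.3).

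**Several values.** SAP 6.2.10 covers continuous ECG data: "if more than one value (for instance, triplicate recordings) is recorded at a time point (i.e., date), the mean value rounded to the integer" is what gets presented. Triplicates are an example there, not a limit. For the overall interpretation, the same section keeps the worst result. SAP 6.2.12 covers several records at one visit: "the scheduled visit will take highest precedence, followed by early withdrawal visits, and unscheduled visits last".

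**Output.** SAP 6.12.4 plans descriptive statistics for observed values and changes, QTcF included, and also: "Shift tables in relation to the overall interpretation". SAP 6.3.4 includes the minimum and maximum, and SAP 6.3.6 presents these data by treatment group. All ECGs are listed. The ECG tables are 14.3.6.2 and 14.3.6.3, and neither uses a QTcF threshold.

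**Entry limit.** Protocol 7.2, criterion 8, excludes "QTcF >450 msec (males) or >470 msec (females". It is an exclusion criterion; the protocol sets no on-treatment QTcF limit.

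**The concern.** A same-date averaging rule suits planned triplicates, where every subject is averaged alike. Once scheduled ECGs are single, a second tracing on one date is usually there because the first was abnormal. Averaging is then conditional on a flagged result, and only those subjects' values move, mostly back toward their usual level. The same subject could appear as abnormal and clinically significant in the shift table, which keeps the worst interpretation, and have an unremarkable QTcF in the numeric table. Two programmers could also derive different values from the same data, depending on whether they apply 6.2.10 or 6.2.12.

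The second gap concerns rises that nobody judges clinically significant. They need not be repeated, so they are not averaged, but no threshold-based output compares them between arms. Other safety data get more: SAP 6.12.2 gives laboratory values normal-range shift tables, and SAP 6.2.25 defines a threshold-based listing for liver tests.

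**Working it through.** The documents give no QTcF mean, SD or outlier rate, so there is no plan figure to reproduce. The rules can be set side by side; the sizes below rest on assumptions.

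**1. Which value is analysed after a flagged on-treatment ECG**

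| Situation | SAP 6.2.10 | SAP 6.2.12 |
|---|---|---|
| Same-date repeat, filed with the scheduled visit | mean of both | not applicable |
| Same-date repeat, recorded as unscheduled | mean of both | scheduled (triggering) value |
| Later-date repeat mapped to the same visit | not applicable | scheduled (triggering) value |
| Raised QTcF not judged clinically significant | no repeat required | no repeat required |

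Only the first two rows involve averaging. In the second, the rules disagree and neither is given priority.

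**2. One subject.** Analysed value = (trigger + repeat)/2.
- 480 and 450: 465 msec
- 490 and 450: 470 msec, which is not above 470
- 500 and 450: 475 msec

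If the trigger was the highest value in its arm at that visit, the tabulated maximum can fall too.

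**3. Arm means.** Assumptions: true QTcF N(415, 15) truncated at 465, plus a 20 msec shift; single-tracing SD s; three visits; every first tracing above 470 repeated once on the same date. The expected lowering per visit for true value T is 0.5 × s × φ((470 − T)/s). At T = 460 and s = 10 this is 0.5 × 10 × 0.242 = 1.2 msec for that subject. Simulated over the whole population, the arm mean falls by 0.09, 0.17 and 0.28 msec for s = 8, 10 and 12. As a stress case, take 5 of 100 subjects with a 40 msec excursion at the same visit, each back to normal on repeat. Their contribution to the arm mean falls from 5 × 40/100 = 2.0 to 5 × 20/100 = 1.0 msec.

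**4. Readings above 470 msec.** For s = 10, without rounding, where *removed* means that the two-reading mean is 470 or less:

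| True QTcF | First tracing >470 | Share of these removed by averaging |
|---|---|---|
| 460 | 1 − Φ(1) = 15.9% | 67% (60–76% for s = 12–8) |
| 465 | 1 − Φ(0.5) = 30.9% | 46% (42–51%) |
| 475 | Φ(0.5) = 69.1% | 10% |
| 480 | Φ(1) = 84.1% | 3% |

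In the population of step 3, the true share above 470 is [Φ(3.33) − Φ(2.33)]/Φ(3.33) = 0.9%. With s = 10, 5.7% of subjects exceed 470 on at least one first tracing, and 2.5–2.7% do after averaging (with and without rounding). About 98% of the subjects who drop out of the count have a true value of 470 or less. Among subjects truly above 470, detection falls from 95% to 89–90%.

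The trigger used here is a QTcF above 470, whereas Protocol 9.3.4 uses clinical significance. The 450 msec limit for men was not modelled.

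**The case against.** The case on the other side is substantial, and most of it stands.

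- **Same date is not a given.** Tracings go to central cardiologists and are then reviewed by the investigator (Protocol 9.3.4), so a repeat may well fall on a later date. It is then not averaged, and 6.2.12 keeps the triggering value at that visit.
- **Few QTcF readings are caught.** Many clinically significant abnormalities need not involve QTcF, and a raised QTcF not so judged triggers no repeat.
- **Averaging reduces noise.** In step 4 the averaged share (2.5–2.7%) is nearer the true 0.9% than the first-tracing share (5.7%). A reader might infer that the rule hides real prolongation. The calculation does not show that: most lost exceedances are measurement error in subjects below the threshold.
- **The arms are compared.** A reader might infer that QTcF tail effects are not compared between arms at all. The documents do not support this, because worst-case interpretation shifts, TEAEs and the minimum and maximum are all tabulated by arm, and every ECG is listed.
- **The limits are entry criteria.** Using 450/470 msec on treatment extends them beyond their stated purpose.

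A reader might also infer that baseline is wrong because the screening triplicate normally drops out of it. SAP 6.2.2 is explicit: "Baseline is defined as the last non-missing value (either scheduled, unscheduled or repeat) before the subject receives the first dose of study drug". Screening tracings precede washout of disallowed medication, so adding them would be a trade-off, not the correction of an error.

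What survives is the missing exemption, the unresolved overlap between 6.2.10 and 6.2.12, and the absence of a threshold count.

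**Conclusion.** The point holds in a limited form. As written, SAP 6.2.10 averages a same-date for-cause repeat with the tracing that prompted it, and SAP 6.2.12 can give a different value for the same data. This matters for the individual QTcF and the arm maximum, not for arm means, which move about 0.1–0.2 msec for SD 8–10 msec (0.28 for SD 12). The exceedance figures are illustrative only: they rest on an assumed QTcF distribution, an assumed 20 msec shift, same-date repeats and a trigger of 470 msec, none of which the documents supply.

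The absence of a by-arm QTcF threshold count follows from the text and needs no assumption. It matters most for rises not judged clinically significant: they do not become TEAEs on that account, the interpretation shift states no QTcF criterion, and a maximum describes one subject per arm and visit. This is a cheap improvement to a descriptive safety analysis. It affects neither the sample size nor any efficacy result.

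**What to change.** 1. **SAP 6.2.10 and 6.2.12.** Limit averaging to the protocol-scheduled triplicates. In post-dose by-visit summaries use the scheduled tracing, as 6.2.12 already provides, and list repeats. State that this also governs a repeat on the same date.
2. **SAP 6.12.4.** Add one descriptive table: by arm, the number and percentage of subjects with any on-treatment QTcF above 450 msec (men) or 470 msec (women), using every tracing. Say that the entry limits are only a reporting cut and imply no rule for managing subjects. Because single tracings are noisy (step 4), read the count as a comparison with placebo and not as an absolute rate.

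The cost is a few sentences and one extra table, with no new data. The existing SAP addendum was written after database lock and unblinding and leaves the ECG sections unchanged, so a table added after that point must be labelled post hoc.
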